11.0 Statistical Considerations

11.1 Analysis of Primary Objective

The percent change in mean cortical thickness within regions receiving 30 Gy or more will be calculated from time of the treatment planning CT scan to 3 months post SBRT. This % change will be compared between the patients receiving risedronate and those receiving placebo.

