7.0 Measurement of Effect

7.1 Cortical Thickness Mapping Approach and Radiation Dose Mapping

We will utilize our published novel method of cortical thickness mapping as outlined below.

Ribcage and vertebral cortical thickness mapping will be performed for each patient utilizing the CT scan at time of “simulation” or treatment planning/mapping and routine standard of care follow-up imaging at 3 months, 6 months, 9 months, and 12 months, which would be performed regardless of inclusion on this study.

The bony anatomy of the thorax will be segmented for each CT scan using automated thresholding techniques and manual editing in Mimics (v16.0 Materialise, Leuven, Belgium) for Windows. Individual contours of the entire ribs and vertebral bodies from cervical (C) level C7 through thoracic (T) level T12 will be constructed in treatment planning software.

These contours will be utilized to construct 3D surfaces containing over 100,000 vertices throughout the bony thorax using Stradwin software (v5.0 Cambridge University, Cambridge, England) for Windows.

Our unique cortical bone mapping algorithm relies on a global cortical density measurement, which is factored into a piecewise defined Heaviside step function derived from the convolution of the in-plane and out-of-plane point spread functions (PSFs) of each CT scan.

The global cortical bone density for each CT scan will be determined by collecting density measurements at each vertex. The CT values along a 12 mm line normal to the cortical surface at each of the approximately 50,000 vertices of the 3D rib surfaces will be obtained and applied to the validated Ct.Th estimation model constrained by the cortical density and out-of-plane blur.

Cortical thickness maps will be constructed using the pre-SBRT planning CT scan and 3 month post-SBRT follow up CT scan for each treated patient for evaluation of the primary objective. We will similarly perform this analysis at the 6 months, 9 months, and 12 months post SBRT time points for evaluation of secondary objectives.

The received radiation doses to the surface of the ribcage at each vertex will be obtained in MIM and then registered to the corresponding Ct.Th map using iterative closest point (ICP) registration in MATLAB (v2014a, MathWorks, Natick, MA). Each rib will be subdivided into evenly spaced cylindrical subsections (30 subsections per rib) along its centerline using a custom MATLAB algorithm.

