Rib vertices from the pre-SBRT CT scans will be spatially aligned with the post-SBRT CT in 3D Slicer (v 3.6, <http://www.slicer.org>) in Windows to define homologous rib subsections on the post-SBRT CT scan. A rigid transform consisting of translation and rotation operations will be computed and applied to align the pre- and post- treatment ribcage surfaces. A series of approximately twenty-five points will be manually selected on the ribcage surface to derive each transform. An affine transform will then be computed using an iterative closest point (ICP) algorithm and applied to the transformed ribcage surface to account for geometric interscan variation. The mean dose and Ct.Th for each homologous rib region will be calculated from the Ct.Th and dose measurements at all vertices within that region.

Bone within the treatment field (within the 50% isodose line) will be segmented into homologous regions receiving dose at 10 Gy intervals, of 0-10 Gy, > 10 – 20Gy, >20 – 30 Gy, > 30 – 40 Gy, and >40 Gy, and in each region the mean cortical thickness will be calculated. The % change in cortical thickness will be compared in each region between patients who received risedronate and those who received placebo.

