10.0 Data Management

Data Collection Form	Data Storage Location
Informed consent document	EPIC
Protocol registration form	WISER/OnCore
All CT scans imaging and reports	EPIC/PACS
Adverse event log Appendix E	Oncore
Current Medications (Appendix G)	Oncore
Medication/Placebo administration form (Appendix H)	Oncore
Specific radiation related toxicities Modified CTCAE Chest wall pain Radiation pneumonitis Radiation Fibrosis (Appendix K and the pre-filled AE log)	OnCore
Radiation Treatment Details (Appendix N)	OnCore
Cortical Thickness Change (Appendix O)	OnCore
Urine bone turn over data (Appendix P)	OnCore
Fracture Incidence (Appendix Q)	OnCore
Adverse Events Log	WISER/OnCore
Biomarkers of Bone Turnover Activity	REDCap
Pain-Associated Cytokines	REDCap

Double Blind Design

We will work cooperatively with our IDS pharmacy supplying each patient either a single tablet of risedronate 150 mg or a single tablet of placebo. We will work directly with IDS pharmacy staff [contact], to procure identical placebo tablets as well as procedures for un-blinding and drug masking. As the hospital already has an unrelated protocol utilizing 150 mg risedronate vs placebo, many of these procedures are already in place. Patients will enroll through CDPM and be randomized through OnCore, but the investigator will not have knowledge of the randomization arm to which any patient has been assigned. The dispensing pharmacy will provide blinded samples and only the pharmacy will hold keys to un-blinding. At the conclusion of the study, when all patients have completed 12 months of follow up, the investigators will be unblinded to randomization of each patient.

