11.2 Analysis of Secondary Objectives

11.2.1

Percent change in cortical thickness across all time points

The percent change in mean cortical thicknesses from baseline will be assessed at 3 months, 6 months, 9 months, and 12 months post SBRT separately within regions of bone receiving 0 – 10 Gy, >10 – 20 Gy, > 30 – 40 Gy, and >40Gy. These outcomes will be compared using repeated measures analysis of variance (ANOVA).

11.2.2

Incidence and grade of chest wall pain

The incidence and grade of chest wall pain occurring inside the 50% isodose line will be collected and reported per modified CTCAE v5.0 (Appendix K) at 3 months, 6 months, 9 months, and 12 months post SBRT for all patients. Results will be compared between patients receiving placebo or risedronate. The incidence of G3 or greater chest wall pain will also be correlated with the volume of chest wall receiving at least 30 Gy or greater. The chest wall contour is defined as a 2 cm expansion from lung, from the costovertebral angle to the sternum.

11.2.3

Incidence of rib or vertebral fractures

The incidence of rib or vertebral fractures within the treatment field occurring at any time during the entire course of the study (12 months), will be reported and compared between patients receiving placebo or risedronate.

11.2.4

Urinary excretion of N-telopeptide (NTX)

The concentration of urinary NTX will be assessed at each time point from baseline to the conclusion of the study at 12 months. Results will be directly compared in each group.

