11.4 Power and Sample Size

Per analysis of our retrospective human data and preclinical data, we estimate that the mean cortical thickness for both cases and controls pre SBRT will be approximately 1.35 mm. At 3 months, in the absence of any treatment, we estimate approximately 16.7% loss of cortical thickness to bones to 1.13 mm (thus resulting in a mean change of 0.22 mm in controls) within the treatment field in regions of bone receiving ≥ 30 Gy. Conservatively, if risedronate use limits loss of cortical thickness by at least half on a percentage scale (i.e., expected cortical thickness at 3 months in treatment group 8.4% lower, or 1.24 mm, corresponding to an expected mean change in treatment group of 0.11 mm), and assuming a standard deviation of delta cortical thickness in both treatment and control patients of 0.20,⁴ then with a power of 0.80 and a one-tailed alpha of 0.05, we anticipate that we will need 42 patients per group to achieve desired power to illustrate significantly higher preservation of cortical thickness at 3 months post SBRT.

There is no human data to accurately estimate how significantly risedronate will limit bone loss following SBRT, however in our pre-clinical rodent models, cortical thickness was preserved in all mice receiving risedronate and in two mice cortical thickness increased. We have no mechanistic reason to suspect that risedronate would cause increased bone loss and therefore are utilizing a one-tailed alpha in our calculations.

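### The primary comparison in section 11.1 leaves out baseline cortical thickness, which the planning CT already provides; adjust for it, and state power on the percent-change scale

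*Combined protocol and SAP*

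**What the plan says.** Sections 2.1.1 and 5.1.1 define the primary outcome as percent change in mean cortical thickness, in bone receiving 30 Gy or more, from before SBRT to 3 months after. Section 11.1 repeats that definition and adds "This % change will be compared between the patients receiving risedronate and those receiving placebo". It gives no test, model, covariate or sidedness. Section 11.2.1 does name a method, repeated measures ANOVA, but for the secondary dose-band outcomes.

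Section 11.4 describes the expected effect in percent (16.7% against 8.4% loss) and in mm (0.22 against 0.11). On baseline it says "we estimate that the mean cortical thickness for both cases and controls pre SBRT will be approximately 1.35 mm", with no SD for baseline thickness. The only SD is on the mm scale: "assuming a standard deviation of delta cortical thickness in both treatment and control patients of 0.20". It then concludes: "with a power of 0.80 and a one-tailed alpha of 0.05, we anticipate that we will need 42 patients per group".

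The baseline value is collected anyway. Section 7.1 says "Cortical thickness maps will be constructed using the pre-SBRT planning CT scan and 3 month post-SBRT follow up CT scan for each treated patient". On blinding, section 10.0 says that "only the pharmacy will hold keys to un-blinding", and investigators are unblinded only when all patients have completed 12 months.

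**The concern.** Percent change has baseline thickness in its denominator. If baseline differs between patients, that variation enters the outcome directly, and part of it can be removed with a covariate that has to be computed anyway to form the endpoint. Section 11.1 does not use it.

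The power statement does not settle the matter, because its SD belongs to change in mm and not to the percent change that will be tested. The sample size is set at the smallest number that reaches 0.80, so nothing is in reserve if the percent-scale SD is larger than the simple conversion suggests. What is at stake is the precision of the primary comparison. Bias is not at issue.

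**Working it through.** **Inputs from section 11.4.** Difference 0.22 - 0.11 = 0.11 mm; SD of change 0.20 mm; baseline mean 1.35 mm; difference on the percent scale 16.7 - 8.4 = 8.3 points; one-sided alpha 0.05; 42 per group. Power is from the noncentral t distribution with noncentrality d × √(n/2) and 2n - 2 degrees of freedom.

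**The plan's own figure.** d = 0.11/0.20 = 0.55. With 41 per group power is 0.795; with 42 it is 0.804. The stated 42 is therefore reproduced by an unadjusted one-sided two-sample t-test on mm change. A two-sided 0.05 test would need 53 per group.

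**Percent scale, baseline fixed at 1.35 mm.** SD = 100 × 0.20/1.35 = 14.8 points; d = 8.3/14.8 = 0.56; power at 42 per group is 0.817. Using the rounded mm figures instead (0.11/1.35 = 8.15 points), power is 0.804.

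**How much SD the design tolerates.** At 42 per group, power of 0.80 with a difference of 8.3 points needs an SD of at most about 15.2 points. An SD of 16 gives 0.762 and an SD of 17 gives 0.717.

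**Cost of a useless covariate.** One degree of freedom is lost (81 left), and the variance is multiplied by 1 + 1/(2n - 4) = 1 + 1/80 = 1.0125. On the mm scale power goes from 0.804 to 0.799.

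**Possible gain.** This needs two quantities that are not in the documents: the SD of baseline thickness (s) and the correlation of mm change with baseline (r). Both are assumed. Simulation: baseline normal with mean 1.35 mm and SD s, floored at 0.5 mm; mm change with mean -0.22 or -0.11 and SD 0.20; outcome 100 × change/baseline; 40,000 trials per cell. Power at 42 per group, unadjusted / adjusted for baseline:

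| s (mm) | r = -0.3 | r = 0 | r = +0.3 |
|---|---|---|---|
| 0.05 | 0.811 / 0.832 | 0.806 / 0.801 | 0.800 / 0.832 |
| 0.15 | 0.815 / 0.829 | 0.799 / 0.796 | 0.777 / 0.827 |
| 0.30 | 0.809 / 0.811 | 0.769 / 0.777 | 0.713 / 0.798 |

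At r = -0.5 the values run from 0.814 / 0.890 (s = 0.05) to 0.824 / 0.867 (s = 0.30). The change from adjusting therefore runs from about -0.5 point (0.806 to 0.801) to +8.5 points (0.713 to 0.798). With no treatment effect, in the five cells checked, both tests reject in 0.049 to 0.051 of trials.

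**A different assumption: proportional loss.** If percent change is independent of baseline, with the mm SD held at 0.20, the percent SD is 14.0 to 14.8. For s = 0.05, 0.15 and 0.30, unadjusted power is 0.812, 0.827 and 0.843; adjusted power is 0.809, 0.822 and 0.840. Here adjustment loses 0.3 to 0.5 point.

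**The case against.** The strongest reply is that section 11.4 already settles the essentials: one-tailed alpha with a rationale, the direction, the time point and the effect in percent. An unadjusted t-test follows naturally, is valid under randomisation, and has about 0.82 power on the simplest percent conversion. Section 11.4 also describes loss as a percentage; if loss really is proportional to thickness, adjustment gains nothing. Other prespecified analyses would also fill the gap in section 11.1. All of this stands, and it limits the point to a low-cost gain in precision. Naming the test and carrying the alpha across from section 11.4 are, taken alone, only missing detail.

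It is also true that eligibility (section 3.1.2) requires a tumour within 2 cm of the chest wall, not any bone at 30 Gy or more. The covariate exists only for patients with an evaluable region. The same holds for the outcome, so the adjustment excludes nobody further.

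A reader might infer that the trial is underpowered. The documents do not support that. The lowest figure above, 0.713, with 54 per group needed for an unadjusted test, requires an assumed baseline SD of 0.30 mm together with an assumed correlation of +0.3. At correlations of -0.3 and -0.5, unadjusted power stays above 0.80 in the cells shown. A reader might also infer bias; neither randomisation nor the blinding in section 10.0 gives grounds for it.

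Planned dose could be suggested as a further covariate, since section 7.1 says "The mean dose and Ct.Th for each homologous rib region will be calculated". Nothing in the documents shows that mean dose above 30 Gy predicts thinning, so it is not recommended here.

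**Conclusion.** The point holds as a matter of precision and prespecification. Section 11.1 does not use a baseline measurement that the trial already has for each patient with an evaluable region, and section 11.4 states power for mm change when the endpoint is percent change. The 42 per group is reproducible and not shown to be wrong. Whether it gives 0.80 for the declared endpoint depends on whether the percent-change SD is at most about 15.2 points, which cannot be checked from the documents.

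The benefit of adjustment lies between about -0.5 and +8.5 points of power over the assumed ranges, and is nil or slightly negative if percent loss is independent of baseline. The change is worth making because the possible loss is small and known, while the possible gain is larger, though uncertain.

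**What to change.** Before the pharmacy releases the allocation:

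- **Section 11.1.** State that the primary test is the arm coefficient, one-sided 0.05 as in section 11.4, from a linear model for 3-month percent change, with arm and mean planning-CT cortical thickness in the region receiving 30 Gy or more. Report the unadjusted difference as a supporting analysis.
- **Section 11.4.** Give the SD of percent change from the retrospective data that the section already draws on, and state the power at 42 per group on that scale.

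The objective and the outcome stay as they are, and no new data are needed. The cost is wording in two sections and one degree of freedom.

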11.2 Analysis of Secondary Objectives

11.2.1

Percent change in cortical thickness across all time points

The percent change in mean cortical thicknesses from baseline will be assessed at 3 months, 6 months, 9 months, and 12 months post SBRT separately within regions of bone receiving 0 – 10 Gy, >10 – 20 Gy, > 30 – 40 Gy, and >40Gy. These outcomes will be compared using repeated measures analysis of variance (ANOVA).

11.2.2

Incidence and grade of chest wall pain

The incidence and grade of chest wall pain occurring inside the 50% isodose line will be collected and reported per modified CTCAE v5.0 (Appendix K) at 3 months, 6 months, 9 months, and 12 months post SBRT for all patients. Results will be compared between patients receiving placebo or risedronate. The incidence of G3 or greater chest wall pain will also be correlated with the volume of chest wall receiving at least 30 Gy or greater. The chest wall contour is defined as a 2 cm expansion from lung, from the costovertebral angle to the sternum.

11.2.3

Incidence of rib or vertebral fractures

The incidence of rib or vertebral fractures within the treatment field occurring at any time during the entire course of the study (12 months), will be reported and compared between patients receiving placebo or risedronate.

11.2.4

Urinary excretion of N-telopeptide (NTX)

The concentration of urinary NTX will be assessed at each time point from baseline to the conclusion of the study at 12 months. Results will be directly compared in each group.

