3.1 Inclusion Criteria

- 3.1.1 Patients must be 18 years or older, but there is no upper limit on age of inclusion.
- 3.1.2 Patients must have a peripheral lung tumor that is amenable to SBRT as determined by the treating radiation oncologist. To be classified as a peripheral lung tumor, the tumor edge (the edge of the gross tumor volume or GTV in radiation treatment planning software) must be within 2 cm of the chest wall. This is determined by the treating radiation oncologist. The chest wall is defined as the chest wall musculature or ribs/vertebrae immediately adjacent to the lungs.
- 3.1.3 Patients must have ECOG status of 0-3
- 3.1.4 Patients must have a life expectancy of at least 3 months as determined by the treating radiation oncologist.
- 3.1.5 Patients must have the ability to understand and the willingness to sign an IRB-approved informed consent document.

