6.4 Duration of Follow-up

Follow-up for serious adverse events and mortality after the single dose of 150 mg of risedronate or placebo is administered will take place during the routine clinic visits during radiation treatment. Radiation treatments will occur within 1 – 3 weeks of taking the study drug. The 30 day follow-up window that is part of mandatory DSMC-SAE reporting will be considered 30 days from the end of all treatments of radiation. This visit can be either a phone call or a visit in person to review adverse events and may be conducted and documented in the medical record by either research study staff RNs or the treating physician. A window of +/- 7 business days is allowed for the 30 day followup assessment.

Specific toxicity related to radiation pneumonitis, radiation fibrosis, and chest wall pain will be collected at each followup point as per appendices K – M.

Patients removed from study for unacceptable adverse events will be followed until resolution or stabilization of the adverse event.

Patients will be followed for a minimum of 3 months for assessment of the primary objective.

Patients will be ideally followed in total for 12 months after completion of radiation therapy for the purposes of this study.

In the event that patients develop progressive disease or a new cancer, requiring additional chemotherapy they will be withdrawn from further study directed followup. In these situations, the followup schedules and imaging become dramatically different from what is directed on this protocol. Additionally further systemic chemotherapy treatments can heavily alter bone density/cortical thickness. As such, if patients develop new disease requiring additional systemic chemotherapy treatment outside of their initial SBRT, they will be withdrawn from study for further follow ups/study directed imaging. Any data that was collected prior to study withdrawal will still be used in analysis. **Immunotherapy or**

hormonal therapy for breast or prostate cancer will not be considered reasons for withdrawal.
Cryoablation or radiofrequency ablation will not be considered a reason for withdrawal from study.

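### The repeated measures ANOVA named for the 3–12 month cortical thickness comparison would, in its classical form, drop the earlier scans of withdrawn patients, which Section 6.4 says will be used.

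*Combined protocol and SAP*

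**What the plan says.** Section 11.2.1 takes percent change in mean cortical thickness from baseline as the outcome. It "will be assessed at 3 months, 6 months, 9 months, and 12 months post SBRT separately within regions of bone", by dose band, and then gives the method in one sentence: "These outcomes will be compared using repeated measures analysis of variance (ANOVA"). It names no covariance structure, estimation method, analysis set or rule for missing visits. Nothing elsewhere in Section 11 supplies a missing-data rule or a dropout allowance.

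Section 6.4 sets the follow-up that feeds this analysis:

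- The firm commitment is short: "Patients will be followed for a minimum of 3 months for assessment of the primary objective".
- The full year is an aim: "Patients will be ideally followed in total for 12 months after completion of radiation therapy".
- For patients with new disease that needs systemic chemotherapy, "they will be withdrawn from study for further follow ups/study directed imaging".
- Their earlier data are kept: "Any data that was collected prior to study withdrawal will still be used in analysis".

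Section 3.1 sets the matching entry condition: "Patients must have a life expectancy of at least 3 months".

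**The concern.** Classical repeated measures ANOVA works on a complete patient-by-visit table. A patient withdrawn at month 7 has valid 3- and 6-month scans but no 9- or 12-month scan, and the usual routine removes that patient altogether. Incomplete series are foreseeable here, because eligibility and guaranteed follow-up both stop at 3 months and progression treated with chemotherapy ends imaging.

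Two things are at stake. The first is precision, since scans already obtained would go unused. The second is validity. The comparison would be restricted to patients who stayed alive, free of new chemotherapy and fully imaged for a year, and that selection is made after randomisation. Section 2.2.1 gives this analysis the job of showing whether effects persist, so the restriction falls on the plan's own test of durability.

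**Working it through.** **The plan's own figure.** Section 11.4 plans 42 per group for the 3-month endpoint, from a difference of 0.22 − 0.11 = 0.11 mm and an SD of 0.20 mm, "with a power of 0.80 and a one-tailed alpha of 0.05". The normal approximation gives n = 2(1.645 + 0.842)² × (0.20/0.11)² ≈ 41. The noncentral t calculation gives power 0.795 at 41 and 0.804 at 42, so 42 per group (84 in total) reproduces. It contains no allowance for attrition, and no separate calculation exists for the 3–12 month analysis.

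**Does the classical method refuse incomplete patients?** One data set was simulated with 84 patients, four visits and 30% withdrawn over the later visits. It held 293 scans, and 62 patients had all four visits. A standard repeated measures ANOVA routine rejected it as unbalanced and could be run only on the complete cases. A linear mixed model used all 293 scans from all 84 patients.

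**Assumptions for size.** All 84 patients are scanned at 3 months. A fraction d of those remaining is lost, permanently, in each of the three later intervals. Arms are equal, and within-patient correlation ρ is the same between any two visits. Neither d nor ρ is in the documents, so both are shown as ranges.

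**Patients and scans.**

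- Completers = 84(1 − d)³.
- Scans obtained = 84[1 + (1 − d) + (1 − d)² + (1 − d)³].
- Scans used by complete cases = 4 × completers.

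For d = 10%: completers = 84 × 0.729 = 61.2; scans obtained = 84 × 3.439 = 288.9; scans used = 244.9; discarded = 43.9, or 15%.

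**Variance of the arm difference.** For all observed data, the generalised least squares information is summed over patients, each contributing the inverse covariance of the visits observed. For complete cases only the completers contribute. The SD cancels in the ratio (complete-case variance divided by all-data variance).

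| Loss per interval | 5% | 10% | 15% | 20% |
|---|---|---|---|---|
| Completers of 84 | 72 | 61 | 52 | 43 |
| Scans discarded | 8% | 15% | 23% | 31% |
| Ratio, mean over visits, ρ = 0.5 | 1.13 | 1.28 | 1.46 | 1.67 |
| Ratio, mean over visits, ρ = 0.7 | 1.15 | 1.32 | 1.53 | 1.78 |
| Ratio at 12 months, ρ = 0.5 | 1.05 | 1.10 | 1.14 | 1.19 |
| Ratio at 12 months, ρ = 0.7 | 1.09 | 1.18 | 1.28 | 1.38 |

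The penalty is smallest at 12 months because the same patients are observed there under either method; the mixed model gains only by borrowing from earlier visits. It is largest at 3 months (1.17 to 1.95).

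**A milder assumption.** With 10, 20, 30 or 40% withdrawn in total by 12 months at a constant hazard, complete-case analysis discards about 5, 11, 17 or 24% of the scans obtained. These ratios describe precision alone, as if withdrawal were random; they do not measure selection bias.

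**The case against.** The strongest reply is that the plan never says incomplete patients are excluded. The term repeated measures ANOVA is also used for long-format and mixed-model fits that retain them. A long-format fit to simulated data with 10% loss per interval accepted all 298 scans, although only 65 of 84 patients were complete. Section 6.4 can then be read as instructing the analyst to choose such a fit.

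This stands as far as it goes. A reader might infer that Sections 6.4 and 11.2.1 cannot both be followed, and the documents do not support that: an implementation that keeps incomplete patients satisfies both. What remains is that the ordinary meaning of the named method points the other way, and nothing in Section 11 settles the choice before the data are seen.

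Two further limits also stand. A reader might infer that withdrawn patients' scans are lost to the trial. They are not: the primary comparison in Section 11.1 needs only the planning CT and the 3-month CT, and the scans also serve the fracture assessment. A reader might also extend the point to urinary NTX in Section 11.2.4, but that section names no ANOVA, so the same tension does not arise there.

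Finally, the visit-averaged ratios overstate the cost for persistence. The 12-month row bears more directly on that question and is clearly smaller.

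**Conclusion.** The concern holds as a gap in the specification of one secondary analysis. On the usual reading of the named method, the pre-withdrawal scans that Section 6.4 promises to use would be left out of the 3–12 month comparison, and the arms would be compared only among patients with complete 12-month imaging.

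Under 5–20% loss per interval the discarded share is 8–31% of scans. The variance penalty is 1.13–1.78 averaged over visits and 1.05–1.38 at 12 months, for ρ of 0.5–0.7. All of this rests on assumed attrition, permanent dropout and equal correlation between visits. The size of any selection bias cannot be derived from the documents. The primary result is untouched by withdrawals after month 3, so this should be corrected but does not threaten the trial's main conclusion.

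**What to change.** In Section 11.2.1, replace repeated measures ANOVA with a likelihood-based mixed model for repeated measures, fitted per dose band:

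- Terms: arm, visit, arm-by-visit and planning-CT thickness.
- Unstructured within-patient covariance.
- All observed visits included, with the arm difference reported at each visit.

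State that the model assumes data are missing at random given the observed visits. Add a sensitivity analysis for withdrawal due to progression or death. It is needed because Section 6.4 itself says chemotherapy can alter cortical thickness, so the text should say what thickness after that point is meant to represent.

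The cost is a change of analysis wording and one added sensitivity analysis, with no new data. The small downside is reliance on the missing-at-random assumption, which the model does not remove. If the sponsor also wants this type of model for urinary NTX, the baseline covariate should be baseline NTX, not planning-CT thickness.
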